### **6.3 Visit 2**

- Record concomitant drugs.
- Collect and record information on AEs and any intervention for the AEs (drug and non-drug therapy).
- Perform head imaging (CT or MRI) within 24 hours to 36 hours after the start of study drug administration.
- Perform the NIHSS assessment and record the results at  $24 \pm 4$  hours after the start of study drug administration. Perform vital sign measurement (blood pressure and pulse rate), 12-lead ECG, and hematology, blood chemistry, and blood coagulation (local) tests at  $24 \pm 12$  hours after the start of study drug administration, and record the results.
- Collect blood for a blood coagulation test performed at the central laboratory at 24 hours ( $\pm 10$  minutes) after the start of study drug administration.
- Collect blood for pharmacodynamic assay at 24 hours ( $\pm 10$  minutes) after the start of study drug administration.
- Collect blood for pharmacokinetic assay at 24 hours ( $\pm 10$  minutes) after the start of study drug administration.

### **6.4 Visit 3**

- Record concomitant drugs.
- Collect and record information on AEs and any intervention for the AEs (drug and non-drug therapy).
- Measure vital signs (blood pressure and pulse rate) at  $48 \pm 12$  hours after the start of study drug administration, and record the results.
- Collect blood for pharmacodynamic assay at 48 hours ( $\pm 15$  minutes) after the start of study drug administration.
- Collect blood for pharmacokinetic assay at 48 hours ( $\pm 15$  minutes) after the start of study drug administration.

## 6.5 Visit 4

- Record concomitant drugs.
- Collect and record information on AEs and any intervention for the AEs (drug and non-drug therapy).
- Perform vital sign measurement (blood pressure and pulse rate), and hematology and blood chemistry tests at  $96 \pm 12$  hours after the start of study drug administration, and record the results.
- Collect blood for a blood coagulation test performed at the central laboratory at 96 hours ( $\pm 15$  minutes) after the start of study drug administration.
- Collect blood for pharmacokinetic assay at 96 hours ( $\pm 15$  minutes) after the start of study drug administration.

## 6.6 At the Onset of Intracranial Hemorrhage (If Observed Within 96 Hours after the Start of Study Drug Administration)

- Perform head imaging (CT or MRI).
- Record the NIISS score.

## 6.7 Visit 5 to Visit 6 (Follow-up)

- Perform follow-up twice, namely, on Days  $30 \pm 7$  and  $90 \pm 7$ .
- Collect and record information on AEs and any intervention for the AEs (drug and non-drug therapy).
- Follow-up via telephone, etc., will also be acceptable.
- Record the mRS score.
- Determine the presence or absence of any new cerebrovascular accidents that occur after Visit 4. Record information on the event, if any, including the date of onset and the event term (ischemic stroke, intracranial hemorrhage, and others).

## 6.8 List of Study Procedures

Study procedures and the schedule of each study procedure are shown in Table 6.8-1 and Appendix 1, respectively.

The investigator, subinvestigator, or study staff will determine whether the subject is receiving treatment at another department of the study center or another hospital.

**Table 6.8-1 List of Study Procedures**

Study Procedure	
Informed consent	Date of informed consent
Baseline subject characteristics	Date of birth, sex, the site of occlusion, ASPECTS (score, equipment used [CT or MRI]), complications, medical history of ischemic stroke/TIA and intracranial hemorrhage, concomitant drugs, smoking habit, pregnancy test result (if applicable), and a change in the therapeutic category
Inclusion/exclusion criteria	Compliance with the inclusion/exclusion criteria (If any inclusion/exclusion criteria are not met, provide each relevant criterion, the criterion number, and the protocol version number.)
Physical examination and medical interview	Date of physical examination, the presence or absence of AEs
Height, body weight, and vital signs	Height, body weight, BMI (calculated from the subject's height and body weight), blood pressure, pulse rate
Head imaging	CT or MRI and angiography of the head
ECG	12-lead ECG
Laboratory tests	
Hematology test	Red blood cell count, hemoglobin, hematocrit, white blood cell count, white blood cell differential (neutrophil, lymphocyte, monocyte, eosinophil, basophil), platelet count
Blood chemistry test	Total protein, albumin, A/G ratio, total bilirubin, direct bilirubin, AST, ALT, ALP, $\gamma$ -GT, LDH, CK, BUN, creatinine, uric acid, Na, K, Cl, Ca, P, Mg, total cholesterol, triglyceride, glucose, CRP
Blood coagulation test (local)	PT, INR, aPTT
Blood coagulation test (central)	PT, INR, aPTT, fibrinogen
Neurological Symptoms	NIHSS, mRS
Pharmacokinetics	Plasma and urine drug concentrations
Pharmacodynamics (biomarkers)	TAfIa activity, D-dimer level, TAfI antigen level, and a change in coagulation and fibrinolytic parameters in the fibrin clot structure
Pharmacogenomics	Gene banking

## 6.9 Baseline Subject Characteristics

The investigator or subinvestigator will collect the following information before the start of study drug administration, and record it in the CRF:

- Date of informed consent, date of birth, sex, the site of occlusion, and ASPECTS (score, equipment used [CT or MRI])

After acute-phase treatment, the following information will also be collected and recorded in the CRF as soon as possible:

- Complications (findings/diagnosis and the date of diagnosis), medical history of ischemic stroke/TIA and intracranial hemorrhage, prior treatment/concomitant drugs (the drug name, dosage regimen, start and end dates of treatment, and the reason for use), smoking habit (presence or absence), and a change in the therapeutic category (presence or absence, change, and date of the change)

If there are any changes in the inpatient/outpatient therapeutic category, the following information will be recorded in the CRF:

- Changes in the therapeutic category (change and date of the change)

The investigator, subinvestigator, or study staff will determine whether the subject is receiving treatment at another department of the study center or another hospital.

## **6.10 Physical Examination and Medical Interview**

The presence or absence of AEs before the start of study drug administration and dates of physical examination at Visits 2, 3, 4, 5, and 6 will be recorded in the CRF.

## **6.11 Height, Body Weight, and Vital Signs**

Height and body weight will be measured before Visit 4, and the results and date of measurement will be recorded in the CRF. For blood pressure and pulse rate, the presence or absence of measurements and the results and date/time of measurements will be recorded in the CRF before the start of study drug administration and at Visits 2, 3, and 4.

## **6.12 Pregnancy Test**

A pregnancy test will be performed in premenopausal female subjects before the start of study drug administration. Either a blood test or a urinalysis will be acceptable. The date and result of the test will be recorded in the CRF.

## **6.13 Head Imaging (CT or MRI)**

Diagnostic imaging will be performed before the start of study drug administration, within 24 to 36 hours after the start of study drug administration, and at the onset of intracranial hemorrhage (within 96 hours after the start of study drug administration). The primary objective of this diagnostic imaging is to determine the presence or absence of bleeding. The following information will be recorded in the CRF:

Equipment used (CT or MRI), the date of testing, and the presence or absence of intracranial hemorrhage

The image data need to be submitted to the sponsor for the assessment of intracranial hemorrhage classification by the central adjudication committee member. For subjects transported from another hospital, it is not necessary to obtain new image data if image data for submission are available.

## **6.14 Electrocardiogram**

Findings of 12-lead ECG obtained before the start of study drug administration and at Visit 2 will be assessed as “normal,” “abnormal, not clinically significant,” or “clinically

significant.” The assessment and the date/time of measurement will be recorded in the CRF. If assessed as “clinically significant, it should be determined whether the finding is regarded as an AE. Findings that have already been noted prior to study drug administration and have not worsened after study drug administration will not be regarded as AEs. For findings regarded as AEs, the event will be recorded in the CRF.

## **6.15 Laboratory Tests**

The parameters listed below will be measured before and at 6 hours after the start of study drug administration, at Visits 2 and 4, and at the time of discontinuation, and the presence or absence of measurements, the date/time of blood collection, and the measurement results will be recorded in the CRF. Each study center’s reference ranges will be used for laboratory data.

- Hematology test: red blood cell count, hemoglobin, hematocrit, white blood cell count, white blood cell differential (neutrophil, lymphocyte, monocyte, eosinophil, basophil), platelet count
- Blood chemistry test: total protein, albumin, A/G ratio, total bilirubin, direct bilirubin, AST, ALT, ALP,  $\gamma$ -GT, LDH, CK, BUN, creatinine, uric acid, Na, K, Cl, Ca, P, Mg, total cholesterol, triglyceride, glucose, CRP

## **6.16 Blood Coagulation Test**

Blood coagulation parameters (PT, INR, aPTT, and fibrinogen) will be measured at the central laboratory before and at 6 hours after the start of study drug administration and at Visits 2 and 4. The date/time of blood collection will be recorded in the CRF. For safety confirmation, blood coagulation parameters (PT, INR, and aPTT) will also be measured at each study center before and at 6 hours after the start of study drug administration and at Visit 2, and the presence or absence of measurements, the date/time of blood collection, and the measurement results will be recorded in the CRF. Each study center’s reference ranges will be used for blood coagulation parameters measured at each study center.

## **6.17 Neurological Symptoms (National Institute of Health Stroke Scale)**

The NIHSS assessment will be performed before the start of study drug administration, immediately after thrombectomy device treatment, at  $24 \pm 4$  hours after the start of study drug administration, and at the onset of intracranial hemorrhage, and the NIHSS score and the date/time of assessment will be recorded in the CRF. In the event of intracranial hemorrhage, the NIHSS score and the date/time of assessment should immediately be recorded in the CRF, and it should be confirmed whether the event is a symptomatic intracranial hemorrhage.

## 6.18 Neurological Symptoms (modified Rankin Scale)

The mRS assessment will be performed at Visit 5 (Day  $30 \pm 7$ ) and Visit 6 (Day  $90 \pm 7$ ), and the method, date, and results of assessment will be recorded in the CRF.

**Table 6.18-1 Modified Rankin Scale**

Grade 0	No symptoms at all
Grade 1	No significant disability despite symptoms; able to carry out all usual duties and activities
Grade 2	Slight disability; unable to carry out all previous activities, but able to look after own affairs without assistance
Grade 3	Moderate disability; requiring some help, but able to walk without assistance
Grade 4	Moderately severe disability; unable to walk without assistance and unable to attend to own bodily needs without assistance
Grade 5	Severe disability; bedridden, incontinent and requiring constant nursing care and attention
Grade 6	Dead

## 6.19 Cerebral Artery Revascularization (Mechanical Thrombectomy or Local Intra-arterial Thrombolysis)

For any mechanical thrombectomy or local intra-arterial thrombolysis performed on cerebral arteries at any time between the day of informed consent and Visit 4 (96 hours after the start of study drug administration), the details listed below will be recorded in the CRF.

The date/time of the onset of ischemic stroke, visit, and puncture, the site of puncture, the size of the guiding catheter, the date/time of the initial device delivery (the start of intra-arterial injection), the date/time of recanalization of the occluded vessel, the site of vascular occlusion, the TICI grade (assessment date/time and results), the type of the device used (thrombolytic drugs), and the presence/absence and the type of an additional device.

If the accurate date/time of the onset of ischemic stroke cannot be identified, the date when the subject was last confirmed to be healthy will be recorded. If thrombectomy is considered feasible based on the imaging findings although it is more than 8 hours after the time when the subject was last confirmed to be healthy, it should be recorded.

The TICI grade will be determined according to Table 6.19-1. The image data used for the final assessment will be submitted to the sponsor.

**Table 6.19-1 TICI Grades**

0	No perfusion
1	Recanalization achieved but with no or slow peripheral perfusion

2A	Perfusion achieved in half or less of the vascular territory
2B	Perfusion achieved in half or more of the vascular territory
3	Complete perfusion with peripheral perfusion

## 6.20 Other Surgical Procedures for Cerebrovascular Accidents

For any of the following surgical procedures performed at any time between the day of informed consent and Visit 6 (Day 90), the date/time of the procedure will be recorded in the CRF:

- 1) Carotid artery stenting
- 2) Carotid endarterectomy
- 3) Bypass surgery
- 4) Surgery for cerebral aneurysm (eg, surgical clipping, coil embolization)
- 5) Surgery for intracranial hemorrhage (eg, hematoma evacuation, hematoma aspiration)

## 7. PRIMARY ENDPOINTS

The primary endpoints of this study are the incidences of the following bleeding events, because safety confirmation is the primary objective of this study:

- Symptomatic intracranial hemorrhage confirmed within 36 hours after the start of study drug administration
  - Intracranial hemorrhage with clinical deterioration causing an increase in the NIHSS score of  $\geq 4$  points (defined by ECASS)
- Asymptomatic intracranial hemorrhage confirmed within 36 hours after the start of study drug administration

All events of intracranial hemorrhage other than the above-mentioned symptomatic intracranial hemorrhage, and will be classified as follows:

- 1) Hemorrhagic infarction type 1 (HI1) Small petechial hemorrhage along the margins of the infarct
- 2) Hemorrhagic infarction type 2 (HI2) Confluent petechial hemorrhage within the infarcted area, but without a mass effect
- 3) Parenchymal hematoma type 1 (PII1) Hematoma involving  $\leq 30\%$  of the infarcted area with a slight mass effect
- 4) Parenchymal hematoma type 2 (PH2) Hematoma involving  $> 30\%$  of, or outside the infarcted area, with a significant mass effect

- Non-intracranial (TIMI) major bleeding confirmed within 96 hours after the start of study drug administration
  - Clinically evident bleeding with a 5 g/dL or greater decrease in hemoglobin. A 2-unit (1 unit is equivalent to 200 mL) blood transfusion will be converted to a 1 g/dL increase in hemoglobin.

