The study population consists of patients with acute ischemic stroke in principle within 8 hours after the onset who are not receiving rt-PA therapy, and in whom a thrombectomy device is indicated. Administration of the study drug (the investigational drug or placebo) will in principle be started before recanalization of the occluded vessel after thrombectomy device placement is confirmed (study drug administration will be started immediately if recanalization is achieved before the start of study drug administration). The study drug will be administered as a 6-hour intravenous infusion (25% of the entire amount will be administered intravenously over 30 minutes, followed by 5.5-hour continuous intravenous infusion of the remaining 75% of the injection). Head imaging for assessment of the primary endpoint of intracranial hemorrhage will be performed within 24 hours to 36 hours after the start of study drug administration. As a secondary efficacy endpoint, the change in the NIHSS score at  $24 \pm 4$  hours after the start of study drug administration relative to baseline and the proportion of subjects with good prognosis (mRS score of 0 to 2) on Days 30 and 90 will be assessed (Refer to Figure 3.1-1).

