## 6. STUDY PROCEDURES

### 6.1 Screening and Randomization (Prior to the Start of Study Drug Administration)

- Obtain the subject's signature on the informed consent form (ICF).
- At the study center(s) participating in the gene banking research, obtain the subject's signature on the ICF for the gene banking research (which is optional and will be performed by Visit 4).
- Review inclusion/exclusion criteria.
- Perform head imaging (CT or MRI).
- Record baseline subject characteristics.
- Collect information on complications, concomitant drugs, smoking habit, height, and body weight as far as possible. Any uncollected information should be collected and recorded in the CRF as soon as possible after acute-phase treatment.
- Record the pregnancy test result, as appropriate (the test date and results).
- Record vital signs (blood pressure, pulse rate).
- Perform 12-lead ECG.
- Perform hematology, blood chemistry, and blood coagulation (local) tests.
- Record the baseline NIHSS score.
- Collect blood for the blood coagulation test, and pharmacodynamic and pharmacokinetic assays performed at the central laboratory.

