### 6.2 Visit 1 (Day of Study Drug Administration)

- Administer the study drug, and record the start and end times of study drug administration
- Perform thrombectomy device treatment, and record the details (refer to Section 6.19 "Cerebral Artery Revascularization").
- After the completion of thrombectomy device treatment, record the TICI grade and the NIHSS score obtained immediately after the treatment.
- Collect and record information on AEs and any intervention for the AEs (drug and non-drug therapy).
- Record concomitant drugs.
- Perform hematology, blood chemistry, and blood coagulation (local) tests at 6 hours (-5 minutes) after the start of study drug administration, and record the test results.
- Collect blood for a blood coagulation test performed at the central laboratory at 6 hours (-5 minutes) after the start of study drug administration.
- Collect blood for pharmacodynamic assay at 6 hours (-5 minutes) after the start of

study drug administration.

- Collect blood for pharmacokinetic assay at 0.5 hours (-5 minutes), 3 hours ( $\pm 10$  minutes), and 6 hours (-5 minutes) after the start of study drug administration. Collect blood at 18 hours ( $\pm 10$  minutes) after the start of study drug administration as far as possible.
- Collect urine for 24 hours after the start of study drug administration for pharmacokinetic assay.

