#### **10.4.8 Assessment of Bleeding Adverse Events**

The investigator or subinvestigator will determine whether each AE is a bleeding event, and will record it, with the presence or absence of external factors (with details, if present), in the CRF.

- In case of intracranial hemorrhage

The type of intracranial hemorrhage (symptomatic or asymptomatic), the date/time of the NIHSS assessment (at baseline and onset), and the details of the event will be recorded in the CRF.

- In case of non-intracranial hemorrhage

The presence or absence of a 5 g/dL or greater decrease in hemoglobin, the presence or absence of blood transfusion (with the date/time, name, amount of blood transfusion, and AE(s) requiring blood transfusion, if present), the presence or absence of surgical treatment (with details, if present), and the details of the event will be recorded in the CRF.

The final classification and assessment of bleeding events will be performed by the central adjudication committee member in a blinded fashion. The investigator or

subinvestigator will provide the sponsor with head imaging results used as the basis for assessment.

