## 18. APPENDICES

### 18.1 Schedule of Events

Table 18.1-1 Schedule of Events

Study Period		Screening Randomize	Treatment Period							Follow Up		Dis-continuation g		
Visit			1							2	3	4	5	6
Hour		Predose	0	0.5	3	6	18	24	48	96				
Day											30	90	-	
Informed consent		○												
Baseline subject characteristics		○												
Inclusion/exclusion criteria														
Prior treatment and concomitant drugs		○						○	○	○			○	
Physical examination		○						○	○	○	○ a	○ a	○	
Height/body weight measurement		● b												
Head imaging (CT or MRI)		●						○ c					○ h	
Neurological symptoms	NIHSS	●		○ d				○ d					○ h	
	mRS										○	○		
Vital signs		●						○	○	○			○	
12-lead ECG		●						○					○ h	
Hematology and blood chemistry		●				○		○		○			○	
aPTT, PT, INR		●				○		○					○ h	
PT, INR, aPTT, fibrinogen i		○			○		○		○				○	
TAFIa activity, D-dimer level, fibrin clot structure i		○			○		○	○					○ h	
TAFI antigen level		○			○		○						○ h	
AE reporting			↔										○	
Study drug administration			↔											
Cerebral artery revascularization			○ e	Applicable also to repeated procedures										
Pharmacokinetics (blood) i		○		○	○	○	○	○	○				○	
Pharmacokinetics (pooled urine) i				↔									○ h	
Gene banking				○ f										

●: Data obtained prior to informed consent may be used.

a: Follow-up via telephone, etc., will also be acceptable.

b: Height and body weight will be measured before Visit 4.

c: Head imaging (CT or MRI) at Visit 2 will be performed within 24 hours to 36 hours after the start of study drug administration.

d: The NIHSS assessment will be performed before the start of study drug administration, immediately after thrombectomy device treatment, and at  $24 \pm 4$  hours after the start of study drug administration.

e: Thrombectomy will in principle be performed after study drug administration.

f: Blood specimens for gene banking will be collected from subjects who have given informed consent at a single time point in the inpatient setting.

g: If the study is discontinued after Visit 4, the assessment at discontinuation is not required.

h: These events will take place only if the study is discontinued before 24 hours after the start of study drug administration (Visit 2).

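### Does the unprinted NIHSS reference score make the symptomatic ICH endpoint misclassify bleeds after thrombectomy?

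*Combined protocol and SAP*

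**What the plan says.** Section 7 makes symptomatic ICH a primary endpoint: "Intracranial hemorrhage with clinical deterioration causing an increase in the NIHSS score of" at least 4 points, attributed to ECASS and confirmed within 36 hours of starting study drug. Asymptomatic ICH is every other intracranial bleed, graded HI1 to PH2. Section 12.4.2 repeats the symptomatic definition for the two-event stop and the one-event pause. None of these places says which earlier score the rise is measured from.

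NIHSS is scheduled four times (Section 6.17): before study drug, straight after thrombectomy, at 24 ± 4 hours, and at the onset of any ICH.
- Section 6.1, before dosing: "Record the baseline NIHSS score".
- Section 6.2, once the procedure is finished: "record the TICI grade and the NIHSS score obtained immediately after the treatment".
- Section 6.17, when a bleed occurs: "it should be confirmed whether the event is a symptomatic intracranial hemorrhage". No comparator is named.

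The one place that puts NIHSS scores beside the ICH type is Section 10.4.8, where the CRF is to hold the type, "the date/time of the NIHSS assessment (at baseline and onset") and the details of the event. The same section gives final classification to a central adjudication committee member working blind.

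On timing, note e of Table 18.1-1 reads "Thrombectomy will in principle be performed after study drug administration", and Section 3.1 says that administration "will in principle be started before recanalization of the occluded vessel after thrombectomy device placement is confirmed".

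**The concern.** A procedure meant to lower the NIHSS score normally sits between the baseline score and any later bleed. If the rise is taken as onset minus pre-dose baseline, a patient who improves by k points has to worsen by k + 4 before the bleed counts as symptomatic. The opposite error is also possible: a patient who worsens by 4 points for another reason and later has a silent bleed is already at +4.

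The consequences would reach beyond one table. Symptomatic and asymptomatic ICH are two of the three primary endpoints and divide the same bleeds, so one misfiled event lowers one incidence and raises the other. The symptomatic definition also feeds the two-event stop and one-event pause in Section 12.4.2 and, until three active subjects aged 81 or older are enrolled, the 36-hour check in Section 12.4.1. Only subjects are blinded (5.1.3), there is no data monitoring committee (12.4.4, 16.10), and Cohorts 2 to 4 have 12 active subjects each, so a single event can matter.

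**Working it through.** The documents give no stopping probability or misclassification rate to reproduce. The check therefore applies the printed definition to score sequences, then asks how much could be at stake.

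**1. Subtraction against the full definition.** The scores are illustrative.

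| Pre-dose | After thrombectomy | At bleed | Onset − pre-dose | Onset − post-procedure | Worsening with the bleed? |
|---|---|---|---|---|---|
| 17 | 8 | 15 | −2 | +7 | Yes, 7 points |
| 18 | 8 | 14 | −4 | +6 | Yes, 6 points |
| 18 | 18 | 22 | +4 | +4 | Yes, 4 points |
| 18 | 22 | 22 | +4 | 0 | No |

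A bare subtraction from baseline gives asymptomatic, asymptomatic, symptomatic, symptomatic. The printed definition has a second element: there must be clinical deterioration, and that deterioration must produce the rise. Applied to the last column, it gives symptomatic, symptomatic, symptomatic, asymptomatic. The anomalies in rows 1, 2 and 4 arise only if the deterioration element is ignored.

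**2. Is the subtraction prescribed?** Section 10.4.8 lists what to enter when a bleed occurs. It does not say that the type is the difference between the two assessments. Section 6.17 puts all four scores, with date and time, in the CRF, and Section 12.4.1 has the sponsor obtain the data for safety review. A comparator other than baseline therefore needs no new assessment.

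**3. Would the other comparator be plainly better?** Assume each score varies independently around its true value with SD 1.0, 1.5 or 2.0 and is rounded to an integer. The table gives the probability that onset minus reference is at least 4. The mean difference is d (true worsening at the bleed) against the last pre-bleed score, and d − k against baseline after an improvement of k.

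| Case | Last pre-bleed score | Baseline |
|---|---|---|
| d = 7, k = 4 | 99.2%, 94.9%, 89.1% | 36.5%, 40.8%, 43.0% |
| d = 0, k = 4 | 0.8%, 5.1%, 10.9% | at most 0.4% |
| d = 0, k = −4 | 0.8%, 5.1%, 10.9% | 63.6%, 59.2%, 57.0% |

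These are rates of a score difference, not of meeting the printed definition, because the model has no deterioration term. The last pre-bleed score detects more true worsening, but after earlier improvement it is more exposed to ordinary fluctuation.

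It also needs a known onset. Section 6.3 says "Perform head imaging (CT or MRI) within 24 hours to 36 hours after the start of study drug administration". The 24-hour NIHSS may be taken from 20 to 28 hours, so it can precede that scan and still follow the bleed.

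**4. How much could the stopping rule move?** Let p be the true rate, L the assumed share of symptomatic bleeds not counted, and r = p(1 − L). For n active subjects, P(at least 2) = 1 − (1 − r)^n − n·r·(1 − r)^(n−1). The 16% rate is from Section 12.5, and 4.4% is the thrombectomy-group rate in Section 1.2.2.

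Worked case, n = 12, p = 0.16, L = 0: 1 − 0.84^12 − 12 × 0.16 × 0.84^11 = 1 − 0.1234 − 0.2821 = 0.5945.

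| n, p | L = 0 | 10% | 25% | 50% |
|---|---|---|---|---|
| 12, 16% | 59.5% | 53.3% | 43.1% | 24.9% |
| 12, 4.4% | 9.5% | 8.0% | 5.8% | 2.8% |
| 6, 16% | 24.7% | 21.0% | 15.6% | 7.7% |

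No value of L can be taken from the documents, which give no rate of bleeding after early improvement. The calculation ignores the exclusion of bleeds due to external factors. It also overstates the loss if the cited rates were themselves measured from baseline.

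**The case for a change.** The strongest case for a change is that sites, not only the adjudicator, apply this definition. They enter the ICH type, and the 36-hour check holds back the next subject, yet the protocol names no comparator and no ECASS version. Where it means change from baseline it says so, as for the NIHSS efficacy endpoint in Sections 2.1.2 and 8. The SAP need only be final before database lock (12.6), after the cohort decisions have been taken. Section 10.4.8 has sites send imaging to the sponsor, but no text says which NIHSS scores reach the adjudicator. The mandatory two-event stop has no equivalent automatic trigger if an event is filed as asymptomatic.

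Much of this stands as description. The comparator is unprinted, and two readers could in principle differ. What does not stand is the step from there to a misclassifying endpoint. That step needs readers to set aside the deterioration element and treat a recording item as the rule. It also needs the ECASS definition, the SAP and the Central Adjudication Form (13.2.2) all to be silent or to fix baseline; none can be checked from the text.

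The safeguards are also wider than the symptomatic ICH count. The pause criteria in Section 12.4.2 include an open-ended category of events warranting consideration of discontinuation, with treatment-related SAEs as one example. Cohort review (12.4.1) and sponsor review (16.9) apply as well.

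**Conclusion.** No change to the plan follows. The unprinted reference score is a missing detail that the adjudicator and analysts can settle sensibly from the wording of the definition and from scores already collected. No stated rule is shown to give a wrong answer: under the full definition, a 7-point worsening after recovery reads as symptomatic, and a silent bleed after an unrelated decline does not.

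Choosing the last pre-bleed score over baseline would be a trade-off. It follows a deterioration more closely, but it is more sensitive to score fluctuation, may be less comparable with published rates, and is hard to apply when a bleed is first seen on the routine scan.

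The size of any effect is unknown. The stopping-rule figures show what assumed losses of 10% to 50% would do, and the documents do not support any particular loss. The conclusion rests on the deterioration element being applied as written and on final classification by the blinded adjudicator. It would need revisiting if the adjudication form or SAP turned out to prescribe onset minus pre-dose baseline with no regard to deterioration.
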